4.2 Schedule of Assessments

Patients randomized to receive HyBryte will have assessments and treatment as shown in [Table 2](#).

Table 2: HyBryte Patients: Schedule of Assessments

Activity	Screen	Base-line	Week														
			1	2	3	4	5	6	7	8	9	10	11	12	13	14	16
Clinic visit	X	X	XX	XX	XX	XX	XX	XX	XX	XX	XX	XX	XX	XX	X	X	X
Drug Treatment ^a		X	X	XX													
Informed consent	X																
Entry criteria	X	X															
Medical history	X	X															
Serum HCG (females only)	X	X												X			
Identify index lesions		X															
Interim medical history/AEs			X	X	X	X	X	X	X	X	X	X	X	X	X	X	X
Efficacy assessments ^b		X			X			X			X			X	X	X	X
Safety assessments ^c		X			X			X			X			X	X	X	X
Vital signs		X			X			X			X			X	X	X	X
Physical Exam		X												X			X
Labs ^d		X												X			X

^a Patients will apply HyBryte and come in to clinic 21 ± 3 hours later for light treatments. applications will be done at home twice per week at least 2 calendar days apart except for the second treatment in Weeks 3, 6, 9, and 12 when application should occur following the assessment visit either in the clinic or at home. Patients will have erythema assessment and a dermatologic grading of treated areas before and 10-30 minutes after completion of the light treatment.

^b Efficacy assessments are: mCAILS, mSWAT, PGA

^c Safety Assessments are: SAEQ, SCORD, and collection of AEs

^d Labs are: Clinical hematology panel, Clinical Chemistry panel

Patients randomized to receive Valchlor will be treated as per the Package Insert and will apply a thin film of Valchlor on lesions daily. The Schedule of Assessments for this arm of the study is shown in [Table 3](#).

Table 3: Valchlor Patients: Schedule of Assessments

Activity	Screen	Base-line	Week					
			3	6	9	12	13	14
Clinic visit	X	X	X	X	X	X	X	X
Informed consent	X							
Entry criteria	X	X						
Medical history	X	X						
Serum HCG (females only)	X	X				X		
Identify index lesions		X						
Interim medical history/AEs			X	X	X	X	X	X
Efficacy assessments ^a		X	X	X	X	X	X	X
Safety assessments ^b		X	X	X	X	X	X	X
Vital signs		X	X	X	X	X	X	X
Physical Exam		X				X		X
Labs ^c		X				X		X

^a Efficacy assessments are: mCAILS, mSWAT, PGA

^b Safety Assessments are: SAEQ, SCORD, and collection of AEs

^c Labs are: Clinical hematology panel, Clinical Chemistry panel

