
Methodology: This will be an open-label trial enrolling patients with CTCL (stage IA, IB, or IIA) randomized to receive topical HyBryte or topical Valchlor for 12 weeks.
 
Patients randomized to HyBryte will apply the drug to all accessible lesions twice per week followed by visible light treatment 21 (± 3) hours later starting at 6 J/cm² and titrated up at each visit until there is evidence of mild erythema of the treated lesions following the light session (Grade 1 erythema on the Erythema Score) and dropping the light dose if there is Grade 2 erythema. Should the patient have Grade ≥ 3, treatment will be suspended for 1 week and treatment may be restarted at a 1 J/cm² lower than the last well-tolerated light dose.
 
Patients randomized to Valchlor will receive commercially available drug applied as per the package insert.
 
Three to 5 prospectively identified index lesions will be evaluated for mCAILS assessment and the lesions chosen will be representative of the patient's overall disease and, if the patient has both patch and plaque lesions, the index lesions should include each type in the approximate same percentage as their total lesions.
 
Patients will be treated for a total of 12 weeks, with follow-up visits at Week 13, Week 14, and Week 16/End of Study. Every three weeks, patients will come to the clinic for an assessment visit (ie, at Week 3, Week 6, Week 9, and Week 12). At these evaluation visits, a cumulative mCAILS, modified Severity-Weighted Assessment Tool (mSWAT), Physician Global Assessment (PGA), Skin Adverse Event Questionnaire (SAEQ) will be completed, and Scoring Dermatitis (SCORD) collected.
 
For HyBryte patients, these assessments will be done immediately prior to light treatment at the second light treatment visit of the evaluation week (ie, Weeks 3, 6, 9, 12).
 
Follow-up assessments will be conducted at Week 13 (1-week post-treatment), Week 14 (2 weeks post-treatment), and Week 16/End of Study (4 weeks post-treatment) and will also include mCAILS, mSWAT, PGA, SAEQ, and SCORD assessments.
 
Physical examinations and safety labs (hematology and chemistry) will be analyzed at Baseline, at the Week 12 assessment visit, and 4 weeks after completion of therapy (Week 16/End of Study). AE's will be recorded throughout the study. Vital signs will be collected at Baseline and Weeks 3, 6, 9, 12, 13, 14 and 16.
		

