4 STUDY PLAN

4.1 Study Design

This is a randomized, pilot study assessing outcomes of patients receiving HyBryte compared to Valchlor in patients with stage IA, IB, and IIA CTCL. Subjects will be randomized to 12 weeks of treatment with either HyBryte or Valchlor in a 1:1 ratio. Subjects randomized to HyBryte will apply HyBryte to all accessible lesions followed 21 (± 3) hours later by visible light treatment twice per week using the Daavlin 7 Series Phototherapy Device. Treatments will continue twice per week (at least 2 calendar days apart) for a total of 12 weeks of treatment (24 actual treatments). Patients randomized to Valchlor will receive treatment for 12 weeks with Valchlor following the directions in the FDA-approved package insert.

Patients will come to the clinic for an assessment visit at Baseline, Week 3, Week 6, Week 9, and Week 12. Patients will have mCAILS scores collected on their 3 to 5 index lesions, an mSWAT score, PGA, SAEQ completed, and a SCORD score collected.

For patients randomized to HyBryte, the assessments will be conducted immediately prior to light treatment at the second light treatment visit of the evaluation week (ie, Week 3, 6, 9, 12) immediately prior to the corresponding light treatment.

Patients will return to the clinic for follow-up visits and have assessments (mCAILS, mSWAT, PGA, SAEQ, and SCORD) at Week 13, Week 14, and Week 16/End of Study.

Safety laboratory assessments and physical exams will be done at Baseline, the Week 12 assessment visit, and the Week 16/End of Study visit. Vital signs will be collected at Baseline and Weeks 3, 6, 9, 12, 13, 14 and 16. Adverse events will be collected throughout the study.

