6.2.2 Baseline

At the Baseline visit, the following will be done prior to randomization:

- Confirmation that the patient meets all inclusion/exclusion criteria
- History of any medical changes obtained
- Women of child-bearing potential will have a serum pregnancy test obtained unless the screening test was obtained 7 days or less
- Physical exam
- Vital signs obtained
- Blood for the hematology panel obtained
- Blood for the clinical chemistry panel obtained
- Three to five lesions that are representative of the patient's disease and are discrete with defined borders, will be chosen as the index lesions, and classified as patch or plaque lesions
- Charting of all CTCL lesions on the "Body Lesion Diagram" ([APPENDIX III – Body Lesion Diagram](#)) locating and numbering each of the index lesions
- Each index lesion will have an mCAILS score assessed and recorded
- The mSWAT score will be assessed and recorded
- The SAEQ score will be collected and recorded
- The SCORD score will be collected and recorded

Once all of these assessments are completed, the patient will be randomized into one of the two treatment arms, to receive HyBryte or Valchlor as the study drug. Patients who are randomized into the HyBryte treatment arm will follow the assessments outlined in Section [6.2.3](#). Patients who are randomized into the Valchlor treatment arm will follow the assessments outlined in Section [6.2.4](#).

6.2.3 *HyBryte Patients*

Patients who are randomized into the HyBryte treatment arm will be given a jar of ointment at the Baseline visit. They will be instructed on proper drug application and demonstrate proficiency in drug application and all accessible lesions will be treated with study drug.

6.2.3.1 *Standard light treatment clinic visits*

Patients randomized to HyBryte will have HyBryte applied twice weekly and an opaque covering applied for 21 (± 3) hours followed by the administration of visible light encompassing wavelengths of 500 to 650 nm. The light will be administered with a precisely calibrated device with a light dose starting at 6 J/cm² twice weekly that is titrated up according to the physician's discretion on subsequent sessions. Treatment will target a post-light treatment Erythema score of 1. The light dose will be reduced, maintained or treatment administrations may be suspended if a Grade 2 or greater erythema is present. Additional assessments of treated lesions and surrounding areas will include:

- Erythema
- Pain
- Pruritus

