6.2.3.2.1 Light Treatment Day

The patient will return to the clinic 21 (± 3) hours after study drug is applied and the following assessments will be conducted prior to light treatment:

- Each index lesion will have an mCAILS score assessed and recorded
- The mSWAT score will be assessed and recorded
- The PGA score will be assessed and recorded
- The SAEQ score will be collected and recorded
- The SCORD score will be collected and recorded

Once the assessments are completed, the standard light treatment procedures will be conducted, as follows:

- Interval medical history obtained
- Any AEs documented
- Adequate application of the drug will be verified by a pink staining on visual inspection of lesions
- Delivery of light session, the time of treatment calculated by the target dose
- A dermatologic assessment of treated lesions will be performed immediately before and 10 to 30 minutes following completion of the light session. This includes assessment of treated lesions and surrounding areas for:
 - Erythema

- Pain
- Pruritus
- Edema
- Hyperpigmentation
- Hypopigmentation
- Rash
- Vesication

6.2.3.3 Week 12 Session 24

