6.2.3.3.1 Light Treatment Day

The patient will return to the clinic 21 (± 3) hours after study drug is applied and the following assessments and procedures will be conducted **prior to** light treatment:

- Each index lesion will have an mCAILS score assessed and recorded
- The mSWAT score will be assessed and recorded
- The PGA score will be assessed and recorded
- The SAEQ score will be collected and recorded
- The SCORD score will be collected and recorded
- Physical Exam
- Vital Signs obtained
- Blood for the hematology panel obtained
- Blood for the clinical chemistry panel obtained

Once the assessments are completed, the standard light treatment procedures will be conducted, as follows:

- Interval medical history obtained
- Any AEs documented

- Adequate application of the drug will be verified by a pink staining on visual inspection of lesions
- Delivery of light session, the time of treatment calculated by the target dose
- A dermatologic assessment of treated lesions will be performed immediately before and 10 to 30 minutes following completion of the light session. This includes assessment of treated lesions and surrounding areas for:
 - Erythema
 - Pain
 - Pruritus
 - Edema
 - Hyperpigmentation
 - Hypopigmentation
 - Rash
 - Vesication

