7 DESCRIPTION OF STUDY PROCEDURES

7.1 Efficacy Assessments

7.1.1 ***Modified Composite Assessment of Index Lesion Severity (mCAILS)***

mCAILS score will be calculated by assessing the erythema, scaling, plaque elevation and involved surface area using the grading scale shown in [Table 5](#), [Table 6](#), [Table 7](#), and [Table 8](#) for each of the index lesions. Each of the assessments and the total score for each evaluated lesion will be recorded in the Case Report Form (CRF). The total mCAILS score will be calculated by adding the scores of all evaluated lesions together.

Table 5: Composite Assessment of Index Lesion Severity – Erythema

Score	Description
0	No evidence of erythema, possible brown hyperpigmentation
1	*
2	Mild: Light red lesion
3	*
4	Moderate: Red lesion
5	*
6	Severe: Very red lesion
7	*
8	Very severe: Extremely red lesion

* Intermediate intervals 1, 3, 5, and 7 are to serve as mid-points between the defined grades 0, 2, 4, 6, and 8

Table 6: Composite Assessment of Index Lesion Severity – Scaling

Score	Description
0	No evidence of scaling on lesion
1	*
2	Mild: Mainly fine scales: lesion partially covered
3	*
4	Moderate: Somewhat coarser scales: lesion partially covered
5	*
6	Severe: Coarse, thick scales; virtually all of the lesion covered; rough surface
7	*
8	Very severe: Coarse, very thick scales; all of the lesion covered very rough surface

* Intermediate intervals 1, 3, 5, and 7 are to serve as mid-points between the defined grades 0, 2, 4, 6, and 8

Table 7: Composite Assessment of Index Lesion Severity – Plaque Elevation

Score	Description
0	0 mm: No evidence of plaque above normal skin level
1	Mild elevation
2	Moderate elevation
3	Marked elevation

Table 8: Composite Assessment of Index Lesion Severity – Surface Area

Score	Area ^a
0	0 cm ²
1	>0 and ≤4 cm ²
2	>4 and ≤10 cm ²
3	>10 and ≤16 cm ²
4	>16 and ≤25 cm ²
5	>25 and ≤35 cm ²
6	>35 and ≤45 cm ²
7	>45 and ≤55 cm ²
8	>55 and ≤70 cm ²
9	>70 and ≤90 cm ²
10	>90 and ≤110 cm ²
11	>110 and ≤130 cm ²
12	>130 and ≤155 cm ²
13	>155 and ≤180 cm ²
14	>180 and ≤210 cm ²
15	>210 and ≤240 cm ²
16	>240 and ≤270 cm ²
17	>270 and ≤300 cm ²
18	>300 cm ²

^a Longest diameter and the longest diameter perpendicular to this diameter of each index lesion will be measured to the nearest millimeter. The lesion area will be the product of these two diameters

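### Table 2 footnote a puts the Week 3, 6, 9 and 12 HyBryte application after the assessments; the synopsis, Section 4.1 and Section 6.2.3 put it 21 (±3) hours before them

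*Combined protocol and SAP*

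**What the plan says.** Footnote a to Table 2 has HyBryte patients apply ointment at home and attend for light 21 ± 3 hours later, twice a week, "except for the second treatment in Weeks 3, 6, 9, and 12 when application should occur following the assessment visit". For that second treatment the footnote allows application in the clinic or at home.

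Five other statements give a different order:

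- Synopsis, Methodology: "For HyBryte patients, these assessments will be done immediately prior to light treatment at the second light treatment visit of the evaluation week".
- Synopsis, Duration of treatment: the same instruction.
- Section 4.1: "the assessments will be conducted immediately prior to light treatment at the second light treatment visit of the evaluation week".
- Section 6.2.3.2.1 (Weeks 3, 6 and 9): "The patient will return to the clinic 21 (± 3) hours after study drug is applied and the following assessments will be conducted" before light is given.
- Section 6.2.3.3.1 (Week 12): "The patient will return to the clinic 21 (± 3) hours after study drug is applied and the following assessments and procedures" are again completed before light.

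At the same light visit, Section 6.2.3.2.1 requires that "Adequate application of the drug will be verified by a pink staining on visual inspection of lesions", and Section 6.2.3.3.1 repeats this. Section 7.1.1, Table 5, grades mCAILS erythema from 0 to 8 by how red the lesion is; a score of 2 is "Mild: Light red lesion". Table 5 mentions possible brown hyperpigmentation at score 0 and says nothing about drug staining. Baseline scores come before any HyBryte: "Once all of these assessments are completed, the patient will be randomized into one of the two treatment arms" (Section 6.2.2). The third objective in Section 2 is to learn how timing affects the ease of measuring mCAILS in HyBryte patients.

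**The concern.** Section 4.1 uses the term assessment visit for the visit at which mCAILS, mSWAT, PGA, SAEQ and SCORD are collected, so the footnote cannot be referring to some other event. An assessment cannot both precede the second application of the week and follow it by 18 to 24 hours. The only rule on which text prevails is in Section 8.2, and it covers conflicts with the Valchlor package insert only.

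What is at stake is the state of the lesion when it is scored. Under Section 6.2.3 the rater looks at skin on which pink staining is expected, and the scale being used grades redness. Under the footnote the rater sees the lesion before that application. Week 12 is one of the affected visits, and the comparative objective is set after 12 weeks of treatment. A pilot with an objective about mCAILS timing should fix that timing and record it.

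**Working it through.** No sample size, power or alpha figure is involved. The check sets the statements side by side and counts visits.

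**Order of events at the second treatment in Weeks 3, 6, 9 and 12**

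| Source | Order |
|---|---|
| Table 2, footnote a | assess → apply → 21 ± 3 h → light |
| Synopsis (two places), Section 4.1 | assess at the second light visit, immediately before light; application is therefore already done |
| Sections 6.2.3.2.1 and 6.2.3.3.1 | apply → 21 ± 3 h → assess → light |

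Five statements support the light-day order and one supports the footnote order.

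**Session numbering.** Two sessions a week put the second session of Week w at number 2w: 2 × 3 = 6, 2 × 6 = 12, 2 × 9 = 18 and 2 × 12 = 24. These match the session numbers in the headings of Sections 6.2.3.2 and 6.2.3.3 and the 24 treatments in Section 4.1. The light-day order is therefore internally consistent.

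**Timing difference.** Under Section 6.2.3 the assessment falls 21 − 3 = 18 to 21 + 3 = 24 hours after the second application. Under the footnote it falls before that application. The two differ by at least 18 hours relative to the same dose.

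**Visits needed.** The clinic-visit row of Table 2 marks two visits (XX) in each of these weeks. Under the footnote, the assessment cannot be at the second light visit, because light follows the application by 18 to 24 hours. That leaves two possibilities:

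- A separate third visit in each of the four weeks, which Table 2 does not schedule.
- The first light visit of the week, which contradicts all five other statements. If ointment were then applied in the clinic at that visit, the two applications would be only about 18 to 24 hours apart, against the two-calendar-day spacing in Section 4.1.

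**Extent.** Efficacy assessments after Baseline are at Weeks 3, 6, 9, 12, 13, 14 and 16, which is 7. The conflict touches Weeks 3, 6, 9 and 12: 4 of 4 on treatment and 4 of 7 (57%) overall. With approximately 10 patients randomised 1:1, about 5 receive HyBryte, so about 5 × 4 = 20 of 5 × 7 = 35 patient-visits are involved.

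**Which scores a stain could reach.** Erythema carries at most 8 of the 8 + 8 + 3 + 18 = 37 mCAILS points per lesion (Tables 5 to 8). Redness is one of five SCORD severity items, each scored 0 to 3 (Appendix II). The documents give no route by which staining would affect mSWAT, which rests on lesion type and area, or PGA.

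**What is recorded.** Section 8.5 has site staff note pink staining as evidence of application. No section asks for the clock times of application and assessment, and Section 7.1.1 does not say how to grade redness on stained skin.

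**The case against.** The strongest reply is that nobody at the site would be misled. Five statements agree, including the two step-by-step procedure sections, which name the session and put the assessments before light. Table 2 itself shows two visits a week. The trial has one centre, with on-site training on procedures and visit schedules (Section 14.1.2). It is an open-label pilot of about 10 patients with no formal efficacy statistics. Most of this stands. A reader might infer that the timing is simply undefined; the documents do not support that, because the intended order can be recovered. What remains is that the footnote is a specific exception naming four weeks, it sits in the schedule of assessments, and nothing in the protocol overrides it.

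A reader might also infer that the footnote gives unstained lesions and Section 6.2.3 stained ones. That is not established. No section says how long staining lasts or requires it to be washed off, so lesions scored under the footnote could still carry stain from the first application of the week.

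Nor is the footnote clearly the fairer comparison with Valchlor. Valchlor is scored before that visit's application (Section 6.2.4) but is applied once daily, so those patients would normally be about a day past their last dose. That is close to the 18 to 24 hours in Section 6.2.3.

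**Conclusion.** The contradiction is real, is in current text, and should be corrected. It is a wrong operating instruction in one clause. If followed, it would change when all 4 on-treatment HyBryte assessments are made relative to dosing, or require an unscheduled visit. The five concordant statements make the light-day order the likely intent.

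No numerical bias can be stated. It is tempting to convert staining into a shift in percent mCAILS reduction, but that needs a stain effect per lesion and a baseline lesion score, and the documents give neither. Percent reduction is also not defined as an endpoint in Section 3 or Section 11.1. If staining has no effect on the redness grades, what remains is the conflicting instruction and its bearing on the third objective. It would also be too strong to say that this objective cannot be met: the light-day order fixes timing within 18 to 24 hours, and mCAILS is repeated 1, 2 and 4 weeks after treatment. The objective is weakened if sites mix the two orders and the times are not recorded. The Week 13, 14 and 16 assessments are not affected.

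**What to change.** 1. In Table 2, footnote a, delete the exception for the second treatment in Weeks 3, 6, 9 and 12. The light-day order in the synopsis, Section 4.1 and Section 6.2.3 then applies throughout, with the two weekly visits already in Table 2.
2. In Sections 6.2.3.2.1 and 6.2.3.3.1, add a line to record the time of application, the time of assessment and whether each index lesion is visibly stained.
3. In Section 7.1.1, add one sentence on how to score erythema when the lesion is stained.

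The cost is one deleted clause, two record lines and one scoring sentence. No visit, sample-size or analysis change is needed. Scoring the same lesions before and after an application would be a new design element, and resolving the contradiction does not require it.

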5 POPULATION

5.1 Number of Subjects

Approximately 10 patients will be randomized 1:1 into the HyBryte: Valchlor arms.

5.2 Inclusion Criteria

In order to be enrolled into the trial, subjects must meet ***all*** of the criteria below:

1. ≥ 18 years of age
2. Minimum of 3 active treatment-accessible CTCL lesions
3. Subjects must have a clinical diagnosis of cutaneous T-cell lymphoma (CTCL, mycosis fungoides), Stage IA, IB, or Stage IIA
4. Subjects willing to follow the clinical protocol and voluntarily give their written informed consent
5. Female subjects not pregnant nor nursing and willing to undergo a pregnancy test within 30 days prior to treatment initiation

5.3 Exclusion Criteria

In order to be enrolled into the trial, subjects cannot have any of the following criteria:

1. History of severe allergic reaction to any of the components of HyBryte or mechlorethamine (Valchlor)
2. Pregnancy or mothers who are breast-feeding
3. All women of childbearing potential (WOCBP) and males with female partners who are WOCBP not willing to use effective contraception
 - a. Women are considered to be WOCBP following menarche and until becoming post-menopausal unless permanently sterile (hysterectomy, bilateral salpingectomy and bilateral oophorectomy). A postmenopausal state is defined as no menses for 12 months without an alternative medical cause. Effective contraception methods for WOCBP should be started prior to randomization and continued for a minimum of 35 days following completion of study drug administration.

b. Acceptable contraceptive methods for WOCBP are those that achieve a failure rate of less than 1% per year and include:

- i. Combined (estrogen and progestogen containing) hormonal contraception associated with inhibition of ovulation:
 - (1) Oral
 - (2) Intravaginal
 - (3) Transdermal
- ii. Progestogen-only hormonal contraception associated with inhibition of ovulation:
 - (1) Oral
 - (2) Injectable
 - (3) Implantable
- iii. Intrauterine device (IUD)
- iv. Intrauterine hormone-releasing system (IUS)
- v. Bilateral tubal occlusion
- vi. Vasectomised partner
- vii. Sexual abstinence defined as refraining from heterosexual intercourse during the entire period of risk associated with the study treatments

c. Male subjects should use condoms during treatment and for 98 days following the last study drug administration period.

4. Subjects with history of sun hypersensitivity or photosensitive dermatoses (eg, porphyria, systemic lupus erythematosus (SLE), Sjogren's syndrome, etc.)
5. Subjects whose condition is spontaneously improving
6. Subjects receiving Valchlor (or any topical compound containing Mechlorethamine) in the preceding 2 months
7. Subjects receiving topical steroids or other topical treatments (eg, tretinoin gel) on treatment accessible lesions for CTCL within 2 weeks of enrollment

8. Subjects receiving systemic steroids, psoralen ultraviolet A (UVA) radiation therapy (PUVA), narrow band ultraviolet B (UVB) light therapy (NB-UVB) or carmustine (BCNU) or other systemic therapies for CTCL within 3 weeks of enrollment
9. Subjects who have received electron beam irradiation within 3 months of enrollment
10. Subjects with a history of significant systemic immunosuppression
11. Subjects taking other investigational drugs or drugs of abuse within 30 days of enrollment
12. Subject has any condition that, in the judgment of the PI, is likely to interfere with participation in the study
13. Subjects receiving drugs known to cause photosensitization within 2 weeks of starting HyBryte therapy unless they have not had evidence of photosensitization after receiving a stable dose of the medication for a minimum of 4 weeks

